Appendix B: Foreseeable and anticipated adverse events related to RF ablation

Anticipated Adverse Events	
1.	Acute Respiratory Distress Syndrome (ARDS)
2.	Air embolism
3.	Allergic reaction / anaphylactic shock
4.	Anemia
5.	Anesthesia reaction (e.g., hair loss)
6.	Apnea - sedation induced
7.	Arrhythmias: bradycardia, tachycardia, pro-arrhythmias, ventricular tachyarrhythmia / pro-arrhythmia
8.	Aspiration pneumonia
9.	Asthmatic attack
10.	Atelectasis
11.	Atrial fibrillation or other arrhythmia: exacerbation of pre-existing arrhythmia
12.	Atrio-Esophageal fistula
13.	Atypical left atrial flutter
14.	AV fistula
15.	Bleeding complications
16.	Bleeding requiring transfusion
17.	Cardiac arrest
18.	Cardiac perforation / Tamponade
19.	Cardiac thrombo-embolism
20.	Cerebro-vascular accident (CVA) / stroke
21.	Chest pain/discomfort
22.	Complete heart block, temporary or permanent
23.	Conduction block: ongoing / resolved
24.	Congestive Heart Failure
25.	Coronary artery dissection
26.	Coronary artery occlusion
27.	Coronary artery spasm
28.	Coronary artery Thrombosis
29.	Death
30.	Deep venous thrombosis
31.	Dislodgement of ICD (Implantable Cardioverter Defibrillator) or permanent pacing leads
32.	Disseminated Intravascular Coagulation
33.	Dyspnea
34.	Endocarditis
35.	Epistaxis
36.	Esophageal injury
37.	Expressive aphasia
38.	Fainting
39.	Fatigue
40.	Gastro-intestinal disorders like gastric reflux, nausea
41.	Gastrointestinal diverticulosis

QDOT MICRO Protocol Version 2.0 17-Nov-2017

Protocol #-MQDT-166

(THERMOCOOL SMARTTOUCH® SF-5D)

Anticipated Adverse Events	
42.	Heart Failure
43.	Hematoma (local) / ecchymosis
44.	Hemorrhage
45.	Hemothorax
46.	High / increased creatinine phosphokinase (CPK)
47.	Hypotension
48.	Hypoxia
49.	Implantable cardioverter-defibrillator (ICD) lead malfunction
50.	Increased phosphokinase level
51.	Infection, localized or systemic
52.	Laceration
53.	Leakage of air or blood into the lungs or other organs due to perforation
54.	Liver toxicity
55.	Mobile strands in Inferior Vena Cava
56.	Myocardial Infarction
57.	Neurological disorders (tremor, poor coordination, headache, ...)
58.	Obstruction / perforation / damage to the vascular system
59.	Parkinson's disease
60.	Pericardial effusion resulting in tamponade
61.	Pericardial effusion without tamponade
62.	Pericarditis
63.	Peripheral embolus
64.	Peripheral nerve injury
65.	Peripheral thromboembolism
66.	Phlebitis
67.	Phrenic nerve damage / diaphragmatic paralysis
68.	Pleural effusion
69.	Pneumonia
70.	Pneumothorax
71.	Pseudoaneurysm
72.	Pulmonary edema
73.	Pulmonary edema / Heart failure
74.	Pulmonary embolism
75.	Pulmonary hypertension
76.	Pulmonary toxicity, like acute pulmonary syndrome
77.	Pulmonary vein dissection
78.	Pulmonary vein Stenosis
79.	Pulmonary vein thrombus
80.	Pump failure
81.	Renal failure
82.	Respiratory depression/failure
83.	Retroperitoneal hematoma
84.	Rhabdomyolysis, including produced by body position or propofol
85.	Sedation induced CO ₂ retention with lethargy and cholecystitis
86.	Seizure
87.	Sepsis
88.	Skin burns (due to cardioversion, tape, etc.)

QDOT MICRO Protocol Version 2.0 17-Nov-2017

Protocol #-MQDT-166

(THERMOCOOL SMARTTOUCH® SF-5D)

Anticipated Adverse Events	
89.	Skin discoloration
90.	Skin injury / muscle or connective tissue injury due to body position, electrical cardioversion
91.	Skin rash
92.	Thrombocytopenia
93.	Thromboembolism
94.	Thrombosis
95.	Thyroid disorders
96.	Transient extremity numbness
97.	Transient ischemic attack (TIA)
98.	Unintended complete or incomplete AV, Sinus node, or other heart block or damage
99.	Urinary retention
100.	Urinary tract infection
101.	Urinary tract injury or infection related to the urinary catheter
102.	Valvular damage/insufficiency
103.	Vasovagal reactions
104.	Vision change
105.	Volume overload
106.	Worsening obstructive, restrictive, or other form of pulmonary disease
107.	X-ray radiation injury of skin, muscle and/or organ

Date: 2018.08.03 10:35:14 -07'00'
Adobe Acrobat version: 11.0.10

(Print)

(Sign)

Date

Franchise Head of Regulatory Affairs:

[name]

Digitally signed by [name]
DN: c=US, o=JNJ, ou=Subscribers, cn=[name],
0.9.2342.19200300.100.1.1=332810
Reason: I am approving this document.
Date: 2018.08.03 15:05:47 -07'00'
Adobe Acrobat version: 11.0.10

(Print)

(Sign)

Date

Revision History

Revision Number	Revision Date (DD/MM/YYYY)	Reasons for Revision
Version 1.0		Original Document

Table of Contents

1	Study Design	5
2	Treatment Assignment	5
3	Randomization and Blinding Procedures	5
4	Interval Windows	5
5	Primary and Secondary Endpoint(s) and Associated Hypotheses.....	5
	5.1 Primary Endpoint(s) and associated hypotheses	5
	5.2 Secondary Endpoints and associated hypotheses.....	5
6	Levels of Significance	7
7	Analysis Sets	7
8	Sample Size Justification.....	7
9	Data Monitoring Committee (DMC).....	8
10	Analyses to be Conducted	8
	10.1 General Conventions	8
	10.2 Disposition of Study Subjects	8
	10.3 Demographic and Baseline Characteristics.....	8
	10.4 Primary and Secondary Endpoint Analyses	9
	10.4.1 Acute Device Performance.....	9
	10.4.2 Safety.....	9
	10.4.3 Procedural Data	9
	10.4.4 Investigational Device Performance.....	9
	10.5 Plans for Interim Analysis	9
	10.5.1 Stopping Rules	10
	10.6 Handling of Missing Data	10
	Appendix: Tables, Listings and Graphs Shells	11

1 Study Design

The QDOT MICRO study is a prospective, multi-center, non-randomized clinical study to evaluate the workflow and acute performance of the THERMOCOOL SMARTTOUCH® SF-5D system in patients diagnosed with Paroxysmal Atrial Fibrillation (PAF).

The changes in this document from the protocol are the definitions of safety and effectiveness populations. The study was stopped due to safety reasons after 8 subjects were enrolled and treated under protocol version 1.0 and then the study catheter was re-designed. Therefore, the subjects who were enrolled and treated under protocol version 2.0 were using a different design of the study catheters.

2 Treatment Assignment

All subjects will receive ablation using the THERMOCOOL SMARTTOUCH® SF-5D catheter with temperature sensing capabilities and micro electrodes and CARTO 3 V 6.0 technology. However, the catheter was redesigned after the first 8 subjects were treated.

3 Randomization and Blinding Procedures

The QDOT MICRO study is non-randomized and unblinded, all subjects will receive ablation via the THERMOCOOL SMARTTOUCH® SF-5D system.

4 Interval Windows

Refer to protocol Table 1 for summary of required schedule for subject treatments and evaluations.

5 Primary and Secondary Endpoint(s) and Associated Hypotheses

5.1 Primary Endpoint(s) and associated hypotheses

Acute Device Performance

Acute Device Performance is defined as confirmation of entrance block in all targeted PVs after adenosine and/or isoproterenol challenge.

5.2 Secondary Endpoints and associated hypotheses

- **Safety**

- Incidence of early onset (within 7 days of ablation procedure) primary Adverse Events.

Serious Adverse Events occurring within the first week (7 days) following an ablation procedure with the THERMOCOOL SMARTTOUCH® SF-5D catheter and AE term is one of the adverse events listed, will be considered for Primary Event assessment

Table 1 Primary Adverse Events

• Death
• Atria-Esophageal Fistula*
• Cardiac Tamponade/Perforation*
• Myocardial Infarction
• Stroke/Cerebrovascular Accident
• Thromboembolism
• Transient Ischemic Attack
• Diaphragmatic Paralysis
• Pneumothorax
• Heart Block
• Pulmonary Vein Stenosis*
• Pulmonary Edema (Respiratory Insufficiency)
• Vagal Nerve Injury
• Pericarditis
• Major Vascular Access Complication/Bleeding

* Pulmonary vein (PV) stenosis, atrio-esophageal fistula and cardiac tamponade/perforation that occurs greater than one week (7days) post-procedure shall be deemed Primary AEs.

- Incidence of Serious Adverse Device Effects (SADEs) during follow-up period (3 month)
- **Procedural data**
 - Rate for touch-up RF application post adenosine and/ or isoproterenol challenge
 - Target sites for RF lesion application
 - o Target sites
 - o Number of RF applications per target
 - o Total RF duration per application (sec)
 - Ablation parameters, including but not limited to:
 - o Total RF ablation time
 - o Temperature (generator files)
 - o Contact Force (CARTO® datafiles)
 - o Power (generator files)
 - o Impedance
 - Total Fluoroscopy time/dose
 - Total procedure time

- ECG data

- **Investigational device performance (rating with survey):**

- Contact and stability of catheter
- Signal Quality
- Temperature visualization
- Ease of use

6 Levels of Significance

All data will be summarized by descriptive statistics. No formal statistical inference will be performed.

7 Analysis Sets

The following analysis populations will be used to complete the analyses of data:

Safety Population 1: The Safety population 1 will include all subjects enrolled under protocol version 1.0 who have the investigational device inserted, regardless if RF energy is delivered.

Safety Population 2: The Safety population 2 will include all subjects enrolled under protocol version 2.0 who have the investigational device inserted, regardless if RF energy is delivered.

Effectiveness Population 1: The effectiveness population will include all subjects enrolled under protocol version 1.0 who meet all eligibility criteria and have had the investigational device inserted and underwent ablation with the study catheter under guidance of the THERMOCOOL SMARTTOUCH® SF-5D Module.

Effectiveness Population 2: The effectiveness population will include all subjects enrolled under protocol version 2.0 who meet all eligibility criteria and have had the investigational device inserted and underwent ablation with the study catheter under guidance of the THERMOCOOL SMARTTOUCH® SF-5D Module.

8 Sample Size Justification

This is a clinical feasibility study for evaluation of workflow and acute performance of THERMOCOOL SMARTTOUCH® SF-5D system. This clinical investigation is intended to provide preliminary estimates of workflow and acute outcomes.

Because this study is a feasibility study, there is no statistical power calculation and no hypothesis to be generated. Fifty subjects are deemed sufficient to characterize the workflow and acute outcomes.

Enrollment in the clinical investigation will be approximately 50 evaluable subjects with approximately 10 subjects per investigational site, distributed over approximately 5 centers in Europe. The study catheter was redesigned in protocol v2.0. The total enrollment remains as approximately 50 evaluable subjects combining subjects enrolled under protocol v1.0 and v2.0.

9 Data Monitoring Committee (DMC)

The medical safety officer or designee will review, on regular or urgent basis, all applicable adverse events and deaths. This medical safety officer shall advise about the appropriateness of continuing or terminating the clinical investigation, based upon findings during his review of adverse events and deaths. The overall safety profile of the investigational device will be evaluated by the Sponsor at the end of the trial.

10 Analyses to be Conducted

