8.4 Subject Disposition

The following subject groups are defined:

- **Enrolled subjects**: subjects who have signed and dated the Informed Consent Form
- **Excluded subjects**: subjects who are enrolled but never undergo the insertion of the investigational device. Excluded subjects will not be included in the safety or functionality evaluation of the investigational device.
- **Discontinued subjects**: subjects who are enrolled and have the investigational device inserted but no RF energy is administered by the investigational device. Discontinued subjects will remain in the safety cohort. These subjects will be followed-up until 7 days post-procedure for safety purpose.
- **Evaluable subjects**: subjects who are enrolled and meet the eligibility criteria and who undergo ablation with the study catheter.
- **Lost to Follow-up subjects**: subjects who are enrolled and evaluable, but contact is lost after most recent follow-up visit (despite 3 documented attempts to contact the subject).
- **Withdrawn / Early Termination Subjects**: subjects who withdraw consent for study participation or are withdrawn by the investigator (as described in Section 8.5) or are terminated from the study prior to completion of all follow-up visits.
- **Completed subjects**: subjects who are enrolled and that have not expired, been excluded, discontinued, withdrawn, terminated early or lost to follow-up from the study, prior to the final study visit.

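### Does calling 50 subjects sufficient across two catheter designs leave the redesigned catheter without a justified sample size?

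*SAP*

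**What the plan says.** SAP Section 8 describes a feasibility study with no power calculation and states that "Fifty subjects are deemed sufficient to characterize the workflow and acute outcomes". Its next paragraph sets a target of about 50 evaluable subjects, roughly 10 at each of some 5 European centres, notes the redesign, and adds: "The total enrollment remains as approximately 50 evaluable subjects combining subjects enrolled under protocol v1.0 and v2.0". Protocol Section 11.1 gives the same 50 evaluable subjects and does not mention that two designs make up the total.

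SAP Section 1 gives the history: "The study was stopped due to safety reasons after 8 subjects were enrolled and treated under protocol version 1.0", and as a result "the subjects who were enrolled and treated under protocol version 2.0 were using a different design of the study catheters". SAP Section 2 repeats that "the catheter was redesigned after the first 8 subjects were treated". Section 1 also says that the SAP departs from the protocol in its definitions of the safety and effectiveness populations.

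SAP Section 7 then splits both populations by protocol version. Safety Population 2 is "all subjects enrolled under protocol version 2.0 who have the investigational device inserted, regardless if RF energy is delivered". Effectiveness Population 2 is "all subjects enrolled under protocol version 2.0 who meet all eligibility criteria and have had the investigational device inserted" and who were ablated under guidance of the SF-5D Module. SAP Sections 10.4.1, 10.4.2 and 10.4.4 run acute success, safety and the device survey in these populations, and Section 10.4.3 summarises procedural data in both kinds. Protocol Section 8.4 defines evaluable as "subjects who are enrolled and meet the eligibility criteria and who undergo ablation with the study catheter".

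**The concern.** Sufficiency is claimed for about 50 subjects, the 50 is reached by adding together people treated with two different catheters, and the endpoint analyses take them apart again. No endpoint analysis written out in the SAP uses the combined total. A reader of Protocol Section 11.1 alone would assume 50 subjects with the current catheter, when there may be about 42.

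The redesign followed a safety stop, so the redesigned catheter is the one readers will care about. If the 50 carried a power or precision promise, a shortfall of up to 8 would break that promise for the primary endpoint. If results were pooled without comment, the headline percentage would mix a withdrawn design with its replacement.

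**Working it through.** **Inputs**
- Total evaluable, both versions together: about 50 (SAP Section 8).
- Subjects treated under version 1.0: 8 (SAP Sections 1 and 2).
- Number of those 8 who are evaluable: k, not stated. They are described as enrolled and treated, which does not settle eligibility, so k runs from 0 to 8.
- Power, precision target, hypothesis: none (Protocol Sections 11.1 and 11.3; SAP Sections 6, 8 and 10.1).

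**The plan's own figure.** 10 subjects per site × 5 sites = 50, which matches. No other calculation stands behind it.

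**Implied number for the redesigned catheter.** At a total of exactly 50, n = 50 − k:
- k = 8: 50 − 8 = 42
- k = 4: 50 − 4 = 46
- k = 0: 50 − 0 = 50

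Because the total is approximate, so is this range. Effectiveness Population 2 also requires guidance by the SF-5D Module, so 42 is not a strict floor for it. The next step takes it to equal the version 2.0 evaluable number.

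**What the difference does to the primary endpoint.** When all n subjects succeed, the exact (Clopper-Pearson) two-sided 95% lower limit is 0.025^(1/n):
- n = 42: 91.6%
- n = 46: 92.3%
- n = 50: 92.9%

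The largest change is 92.9 − 91.6 = 1.3 points. With one failure, the exact lower limit is 87.4% for 41/42 and 89.4% for 49/50, a change of 2.0 points on these rounded figures (1.9 from 87.43% and 89.35%). For the first design, 8 successes out of 8 would give a lower limit of 63.1%. That set is small however Section 8 is worded.

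**Safety.** Safety Population 2 requires only that the device was inserted, with no eligibility or RF condition. It is therefore not capped at 50, and the 42-to-50 comparison does not measure its size.

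**What the analyst would do.** Under SAP Sections 7 and 10.4, the analyst reports version 1.0 and version 2.0 subjects separately, each as a number and a percentage. The actual denominator for the redesigned catheter appears in the output without any planned figure being needed.

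**The case for a change.** The strongest argument for a change is that even a descriptive study should attach its sufficiency statement to the group it sets out to estimate. SAP Section 8 promises preliminary estimates, and the estimates of interest concern the redesigned catheter. Disclosing the combination is not the same as stating the size of that group, and subtraction gives 42 only if all 8 earlier subjects are assumed evaluable. A few sentences would settle it without adding patients.

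The factual part of this stands: the expected version 2.0 number is not written down, and Protocol Section 11.1 does not mention the combination. The consequence does not follow. Sufficiency is claimed for describing workflow and acute outcomes in the study overall, and the SAP nowhere says that 50 applies to Effectiveness Population 2. Stating the split would change no population, analysis or reported result.

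Related additions add little. Naming the version 2.0 populations as the main ones changes nothing when both are already reported. Exact intervals would be a reasonable extra, but the plan is deliberately descriptive, and any reader can compute them from the reported counts. Whether a combined safety column is missing cannot be judged, because the SAP Appendix says the table shells are kept separately.

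Changing Protocol Section 11.1 would also need a protocol amendment, with at least the abbreviated approval that Protocol Section 13.2.1 allows for administrative changes. The SAP carries August 2018 approval dates and refers to version 2.0 treatment in the past tense, so a planned number may add little to the denominators the analysis will show.

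**Conclusion.** The observation is accurate, but it is a gap in wording and calls for no change. The redesigned catheter's evaluable number is 42 to 50, assuming a total of exactly 50 and between 0 and 8 evaluable version 1.0 subjects. Going from 50 to 42 lowers the exact 95% lower limit for acute success by 1.3 points when all succeed and by about 2 points with one failure. These figures take Effectiveness Population 2 to equal the version 2.0 evaluable number.

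No stated target is missed, because none was set. The serious version of the problem, an unacknowledged pooling of two designs, is what the version-specific populations in SAP Section 7 guard against. Following the plan as written gives a separate and correctly denominated result for each catheter.

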10.1 General Conventions

All data will be summarized by description analyses. No formal statistical inference will be made.

10.2 Disposition of Study Subjects

The subject accountability and disposition will be summarized and listed for all enrolled subjects.

10.3 Demographic and Baseline Characteristics

Demographic and baseline characteristics will be summarized and listed for all enrolled subjects and will also be summarized separately for subjects enrolled under protocol v2.0. Age at consent will be summarized with number of subjects, mean, standard deviation, median, quartiles, minimum, and maximum. Gender will be summarized with counts and percentages. Baseline Medical History information and baseline medical scores will be summarized with number of subjects, mean, standard deviation, median, quartiles, minimum, and maximum for continuous variables and with counts and percentages for categorical variables.

10.4 Primary and Secondary Endpoint Analyses

10.4.1 Acute Device Performance

Acute success is defined as achieving confirmation of entrance block in all targeted PVs after adenosine and/ or isoproterenol challenge. The number and percentage of subjects who have reached acute success will be summarized. The analysis will be performed in the effectiveness populations.

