Although acute pulmonary vein isolation (PVI) is almost always achieved with RF ablation, AF recurrence is common.⁵ Several studies have correlated inadequate electrode-tissue contact with ineffective RF lesion generation.¹⁹⁻²³ Higher contact force can lead to serious complications such as steam pops, cardiac perforation or esophageal injury.^{21,22,24}

Until recently,^{25,26} there was no reliable mechanism to provide continuous measurement of the direct contact force (CF) between the tip of the RF ablation catheter and the endocardial tissue. In preliminary studies, feedback from the addition of a CF sensor to RF ablation catheters showed a high degree of between- and within-investigator variability in CF, indicating that even with careful catheter manipulation, operators do not have good control over CF.²⁵ Moreover, lower CFs were associated with intermittent contact with tissue and were most often applied at sites with high rates of reconnection.^{25,27,28}

Technology of RF Catheter Ablation

RF energy utilizes a high frequency (350 kHz to 1 MHz) alternating current to cause resistive heating of a narrow rim of tissue that is in direct contact with the electrode tip.²¹ Heating beyond this rim is based on transfer of thermal energy to the surrounding tissues, and is the primary mechanism by which RF lesions are formed.²² Increasing temperature at the electrode-tissue interface increases the lesion size, but if the temperature exceeds 80 to 100°C, coagulum on the electrode tip can form and lead to an abrupt rise in impedance and a marked decrease in tissue heating.²³ The temperature of the electrode-tissue interface, therefore, is a limiting factor to increasing RF lesion size and depth. The Biosense Webster THERMOCOOL SMARTTOUCH® SF family of catheters features two improvements over standard irrigated RF catheters. First, the THERMOCOOL SMARTTOUCH® catheters provide real-time measurement of contact force (CF) between the catheter tip and heart wall, as well as location information, when used with CARTO® 3 Navigation System. A small spring connects the ablation tip electrode to the catheter shaft with a magnetic transmitter and sensors to measure deflection of the spring. The catheter has a high-torque shaft with a bi-directional deflectable tip section containing an array of electrodes which may be used for recording and stimulation purposes.

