6. CLINICAL INVESTIGATION OBJECTIVE

The purpose of this study is to evaluate the workflow and acute performance, during standard electrophysiology mapping and RF ablation procedures, of the THERMOCOOL SMARTTOUCH® SF-5D catheter with temperature sensing capabilities and micro electrodes used in combination with the CARTO® 3 Navigation System with THERMOCOOL SMARTTOUCH® SF 5D Module.

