9.2.3.1.1 General AF Ablation Guidelines

The AF ablation procedures for this study should follow the below sequence:

- Diagnostic catheter placement (discretion of investigator)
- Electrophysiology study (discretion of investigator)
- Transseptal puncture
- Cardioversion if subject is in AF (discretion of investigator)
- A left atrial anatomical map is required prior to the ablation procedure.
 - An anatomical map is not required of triggers outside of the left atrium (e.g., SVC/CS etc.)
- Introduction of the study catheter and study ablation procedure (see section 9.2.3.1.2)
- Post ablation pacing procedure(s) and/or infusion of cardiac medications to induce AF (eg, Isoproterenol 2-20 mcg/min)

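### The primary acute-success percentage leaves out eligible subjects in whom the study catheter was inserted but no RF was delivered, instead of counting them as not achieving block

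*SAP*

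**What the plan says.** SAP 10.4.1 sets a yes/no result per subject: "Acute success is defined as achieving confirmation of entrance block in all targeted PVs after adenosine and/ or isoproterenol challenge". The summary is simple: "The number and percentage of subjects who have reached acute success will be summarized". The analysis set follows: "The analysis will be performed in the effectiveness populations".

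SAP section 7 defines two effectiveness populations, one per protocol version. Both require that subjects meet all eligibility criteria and "have had the investigational device inserted and underwent ablation with the study catheter", under guidance of the SF-5D module. The two safety populations in the same section require only insertion of the device, with or without RF.

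Protocol 8.4 names the group that falls between these sets. Discontinued subjects are "subjects who are enrolled and have the investigational device inserted but no RF energy is administered by the investigational device". The protocol keeps them in the safety cohort and follows them to 7 days. Neither document counts them as acute non-successes or plans an acute-success figure that includes them. Protocol 11.3.1 names no population for this endpoint, so the SAP makes the assignment. The protocol's own effectiveness and evaluable populations (section 11.2) also require ablation.

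**The concern.** The stated purpose is to "evaluate the workflow and acute performance, during standard electrophysiology mapping and RF ablation procedures". That covers the device in use, and use begins at insertion. The primary percentage instead answers a narrower question: was block achieved, given that the case got as far as RF from the study catheter? A subject who never received RF from the catheter did not achieve block with it, yet appears in neither numerator nor denominator.

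The protocol background says: "Although acute pulmonary vein isolation (PVI) is almost always achieved with RF ablation, AF recurrence is common". The percentage among ablated subjects may therefore sit near its ceiling, where one or two subjects left out can be the difference between 100% and a lower figure. Protocol 3.2.3 describes this as the first experience with this catheter and generator together. SAP section 1 records that the study was stopped for safety reasons after 8 subjects and the catheter redesigned. In that setting a reader will want to know what happened in every eligible insertion.

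**Working it through.** **Inputs.** The planned number is about 50 evaluable subjects (Protocol 11.1, SAP section 8), with no derivation. It matches the site plan: 5 centres × 10 subjects = 50. SAP section 8 keeps this total across both protocol versions, and SAP section 1 gives 8 subjects treated under version 1.0. That leaves 50 − 8 = 42 for version 2.0, if all 8 count as evaluable and the total reaches exactly 50.

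Evaluable subjects, as defined in Protocol 8.4, must have been ablated. No-RF subjects therefore do not count towards the target, and 42 is used whatever their number.

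**Assumptions.** Let *d* be the number of eligible subjects with the device inserted and no RF. The documents give no value, so *d* = 0 to 3 is illustrative. Let *f* be the number of ablated subjects without acute success. Underwent ablation is read as at least one RF application, which makes it the complement of the discontinued category.

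**Formulas.** Planned percentage: (42 − *f*)/42. Percentage with no-RF subjects counted as non-successes: (42 − *f*)/(42 + *d*).

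| *f* | Planned | *d* = 0 | *d* = 1 | *d* = 2 | *d* = 3 |
|---|---|---|---|---|---|
| 0 | 42/42 = 100% | 100% | 42/43 = 97.7% | 42/44 = 95.5% | 42/45 = 93.3% |
| 2 | 40/42 = 95.2% | 95.2% | 40/43 = 93.0% | 40/44 = 90.9% | 40/45 = 88.9% |

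Each such subject costs a little over 2 percentage points. Because (42 − *f*)/(42 + *d*) never exceeds (42 − *f*)/42, the direction is fixed.

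**How likely is at least one?** At an assumed no-RF rate *p* per insertion, the chance of one or more in 42 insertions is 1 − (1 − *p*)^42. This gives 34% at *p* = 1%, 57% at 2% and 88% at 5%.

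**Scale against sampling error.** The plan asks for no confidence interval. For orientation, the exact 95% lower limit is 91.6% for 42/42, 87.7% for 42/43, 84.5% for 42/44 and 81.7% for 42/45. One such subject moves the estimate by less than the uncertainty already present at this sample size.

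**The case against.** The strongest case for the plan has four parts.

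- **The set fits the endpoint.** Entrance block is a result of ablation, and both documents consistently require ablation. This stands as a reason to keep the planned analysis. It does not make that figure a summary of all device uses.
- **The excluded subjects are visible elsewhere.** Disposition covers all enrolled subjects (SAP 10.2). Safety analyses and procedural data include the safety populations (SAP 10.4.2 and 10.4.3). Device deficiencies are collected at the procedure (Protocol Table 1). This stands too: nobody is hidden, and a reader may be able to recover *d*. The primary percentage itself is still not adjusted. Whether reasons for no RF are listed cannot be judged, because the table shells are separate.
- **The study is descriptive.** There is no hypothesis, performance goal or inference, so no decision rule turns on 100% against 97.7%, and type I error and power are not involved. This lowers the stakes.
- **A no-RF case may have nothing to do with the device.** This also stands, and it limits what can be claimed.

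On the last point a reader might infer that, because the transseptal puncture and left atrial map come before the study catheter is introduced, stopping before RF must reflect the catheter, generator or interface. The protocol gives an order of steps, not reasons. It leaves room for other causes: clotting time is checked before RF (9.2.1), thrombus imaging may be done on the procedure day (9.1.2.1), and reactions to sedatives or contrast are listed risks (4.1). Nor does it say that a faulty catheter ends the case. If another study catheter were used, the subject would be ablated and remain in the denominator.

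**Conclusion.** The point holds in a limited form. The primary percentage is conditional on RF having been delivered, and no text counts eligible insertions without RF as non-successes. Relative to all eligible insertions, it can only be equal or too high. With 42 ablated and all successful, the gap is 2.3, 4.5 or 6.7 points for 1, 2 or 3 such subjects, and zero if there are none. These figures rest on the 50 − 8 split and an assumed *d*.

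A reader might go further and infer that catheter or system failures never count against acute success. The documents do not support that. A failure after the first RF application leaves the subject in the denominator, where it can count as a non-success. The gap covers only the interval from insertion to first RF. Nor do the documents show that the excluded cases are device-related or how often they occur.

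This is a cheap improvement to the reporting of a descriptive endpoint, not the repair of an invalid analysis.

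**What to change.** Keep the planned analysis and add to SAP 10.4.1, separately for each protocol version: *Acute success will also be summarised in the effectiveness population plus all subjects who meet all eligibility criteria and had the investigational device inserted but received no RF from it. These added subjects are counted as not having achieved acute success, and the reason for no RF is listed for each.* Report the two percentages side by side.

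The safety populations would be the wrong comparison set. They also drop the eligibility and module-guidance conditions, so the two percentages could differ for up to three reasons at once. An ineligible subject ablated successfully would even push the second figure up.

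The cost is a short SAP addition, one table row per protocol version and a short listing. Insertion and RF status are already needed to define the analysis sets; the sponsor should confirm that the reason for no RF is captured. The downside is that a no-RF case unrelated to the device counts against it. The listed reasons and the retained planned figure let the reader see that.
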